### 5.3 Treatment Assignment

Dosing regimen during the treatment phase will be via the INOpulse device.

#### Cohort 1: Placebo

Placebo at a dose setting of 75 mcg/kg IBW/hr for up to 24 hr/day 99.999% Nitrogen [N2] cartridge; change approximately every 12 hours

#### **Cohort 1: iNO 75 mcg/kg IBW/hr**

iNO at a dose setting of 75 mcg/kg IBW/hr for up to 24 hr/day 6.0 mg/L [4800 ppm] NO cartridge; change approximately every 12 hours.

## 5.4 Sample Size

The sample size calculation for this study was performed assuming one interim analysis. The purpose of the interim analysis is to stop the trial for efficacy or futility conclusion or to continue the trial to 150 or 188 patients.

The sample size calculations were performed using following two designs:

- 1) Design1: Group sequential early stopping criteria and
- 2) Design 2: Sample size re-estimation methodology

Design 1: Traditional group sequential design (GSD) alpha spending function  $\Gamma=3$  ([Hwang, Shih, deCani, 1990](#)) is used to control the overall type 1 error at 0.025, 1-sided.

Design 2: This is the "promising zone" sample size re-estimation (SSR) design of [Mehta & Pocock \(2011\)](#), which uses the [Cui, Hung, Wang \(1999\)](#) method of analysis to combine the test statistics for the separate analyses of the IA and post-IA parts of the trial, if the trial does not stop at IA.

The final analysis is via weighted Z statistic using equal weights for the IA and post IA test statistics. It requires  $p < 0.0229$  1-sided for statistical significance to control the overall type 1 error level at 0.025 1-sided with  $\Gamma=3$  error spending function ([Hwang, Shih, deCani 1990](#)).

A sample size of 150 patients (75 in each group) with simulations assuming true underlying mean treatment difference in 6MWD ranging from 30-70 meters and standard deviation from 50-70 meters yielded  $> 87\%$  power for both designs (for all cases except the most extreme case (mean difference of 30 meters and S.D 75, power for this combination was 71%).

The estimated conditional power (CP) and predictive power (PP) based on interim estimated SD and mean differences observed on 75 subjects with a planned final sample size of 150 is shown in ([Table 22](#)).

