The primary statistical test for the primary endpoint will be performed using a repeated measures mixed model with the baseline stratification factor (i.e., the prostanoid usage status) treatment arm, week and treatment-by-week as the fixed effects. As a covariate, baseline 6MWD assessment (defined by the average of two 6MWTs at Week 2 after the completion of the run-in phase) will be included in the model. In case the normality assumption is invalid, the primary efficacy endpoint will be analyzed using the van Elteren test stratified by the prostanoid usage status. Summary statistics will be provided for all study variables with descriptive statistics (number of observations, mean, standard deviation, median, minimum, maximum and from the analysis model the least squares means, SAE's and confidence limits) for numerical (or continuous) variables and with frequency and percentage for categorical variables.

Exploratory analyses will be performed to evaluate the effects of demographics and baseline characteristics on the efficacy response with appropriate statistical methods. Subgroup analyses based on study drug usage, background therapies, demographics and baseline characteristics, as well as other study compliance status will be conducted. Additional statistical methods such as mixed effects model and Cochran-Mantel-Haenszel (CMH) test (for dichotomized response analysis) may be utilized in the exploratory analyses.

Interim analyses will be conducted when data is available from 75 patients. The purpose of the interim analysis is to stop the trial early for efficacy or futility or to continue the trial to 150 or 188 patients (total randomized is higher to account for an anticipated 20% drop out rate). Group sequential early stopping criteria and sample size re-estimation methodology are further described in the statistics section of this protocol. They are constructed to control overall type 1 error at 0.025, 1-sided.

Simulations assuming true underlying mean treatment difference in 6MWD ranging from 30-70 meters and SD's from 50 to 75 meters yielded >87% power for all cases except the most extreme case (mean difference 30 meters and SD 75, for which power was ~71%.

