16.2. Sample Size Determination

Interim Analysis will be conducted by an independent DMC after 18-week 6MWD data are available from 75 patients. The purpose of the interim analysis is to stop the trial for an early efficacy or futility conclusion or to continue the trial to 150 or 188 - patients (total randomized is higher to account for an anticipated 20% dropout rate). Group sequential early stopping criteria and sample size re-estimation methodology are further described in the statistics section of this protocol. They are constructed to control overall type 1 error at 0.025, 1-sided. Simulations assuming true underlying mean treatment difference in 6MWD ranging from 30-70 meters and standard deviations from 50 to 75 meters yielded >87% power for all cases except the most extreme case (mean difference 30 meters and SD 75), for which power was ~71%.

Subjects who do not comply with the required device adherence, as well as who do not meet the study entry criteria at Week 2, will be withdrawn from the study.

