This is the "promising zone" sample size re-estimation (SSR) design of Mehta & Pocock (2011), which uses the Cui, Hung, Wang (1999) method of analysis to combine the test statistics for the separate analyses of the IA and post-IA parts of the trial, if the trial does not stop at IA.

The final analysis is via weighted Z statistic using equal weights for the IA and post IA test statistics. It requires $p < 0.0229$ 1-sided for statistical significance to control the overall type 1 error level at 0.025 1-sided per the $\Gamma = -3$ error spending function (Hwang, Shih, deCani 1990).

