**Table 35: Interim and Final Analysis Rules:**

Category	Rule
Efficacy	At interim analysis (after 75 patients), if the one-sided $p < 0.0046$ then the study will stop for efficacy (Wald Statistics)
Efficacy	At final analysis (after 150 patients or 188 patients depending on CP and PP), if the one-sided $p < 0.0229$ then the study will yield an efficacy conclusion. (based on CHW Statistics)
Futility	At interim analysis, if conditional power (CP) or predictive power (PP) $\leq 10\%$ then the study stops for futility.
Continue	At interim analysis, if $10\% < CP$ and $PP < 57.2\%$ then trial continues to 150 patients.
SSR	At interim analysis, if $57.2\% \leq CP$ or $PP < 80\%$ the sample size is increased to $N=188$ . The lower bound of the promising zone interval was calculated based on the minimum treatment effect needed to achieve 70% or higher CP.
Continue	At interim analysis, if $CP$ and $PP \geq 80\%$ and 1-sided $p > 0.0046$ , then the trial continues to $N = 150$ patients.

This is the "promising zone" sample size re-estimation (SSR) design of [Mehta & Pocock \(2011\)](#), which uses the [Cui, Hung, Wang \(1999\)](#) method of analysis to combine the test statistics for the separate analyses of the IA and post-IA parts of the trial, if the trial does not stop at IA.

The final analysis is via weighted Z statistic using equal weights for the IA and post IA test statistics. It requires  $p < 0.0229$  1-sided for statistical significance to control the overall type 1 error level at 0.025 1-sided with  $\gamma = -3$  error spending function ([Hwang, Shih, deCani 1990](#)).

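### The >87% power claim is written over SD ranges that disagree between SAP and protocol, and it does not hold across either range: at 30 m, power is about 80-83% at SD 65 and 74-77% at SD 70

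*SAP*

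**What the plan says.** SAP 5.4 opens its power statement with "A sample size of 150 patients (75 in each group) with simulations assuming" true differences "ranging from 30-70 meters and standard deviation from 50-70 meters yielded" more than 87% power. It attributes this to both the group sequential design and the re-estimation design. The one exception is a 30 m difference with SD 75, where power is given as 71%.

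Protocol 16.2 has the same claim with another upper limit: "standard deviations from 50 to 75 meters yielded >87% power for all cases except the most extreme case (mean difference 30 meters and SD 75". In that one case it puts power at about 71%. The synopsis agrees with 16.2: "SD's from 50 to 75 meters yielded >87% power for all cases except the most extreme case".

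SAP Table 22, which follows the sentence in 5.4, lists SDs of 50, 60 and 75 m with differences of 30, 40, 50, 60 and 70 m. It reports conditional and predictive power at the interim, not the simulated power. Neither document lists the simulated cells, and neither prints a power for 30 m with SD 65 or SD 70.

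**The concern.** The SAP sentence conflicts with itself, because its only exception (SD 75) lies outside its stated range (50-70). Taken as written, it excludes nothing inside the range, so it covers 30 m with SD 70. It also conflicts with the protocol's range. In both documents a result that appears to come from three SDs is worded as if it held across an interval, and a whole region of lower power is described as one extreme case.

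This is the plan's only statement of unconditional power. A sponsor, DMC member or ethics committee seeing a pooled SD of 65 or 70 m could take it that a true 30 m effect would be missed less than 13% of the time. Thirty metres is also the SAP's own responder threshold (Table 24, analysis 13), so that row of the power statement matters most.

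**Working it through.** **Inputs.** Overall one-sided alpha 0.025 (SAP 5.4: the spending function "is used to control the overall type 1 error at 0.025, 1-sided"). Interim "after 18-week 6MWD data are available from 75 patients" (protocol 16.2), of 150 evaluable, 1:1. Interim efficacy bound one-sided p < 0.0046, z = 2.605 (SAP Table 35: "then the study will stop for efficacy (Wald Statistics"). Final bound z = 1.997 (protocol 16.5: "It requires $p < 0.0229$ 1-sided for statistical significance to control the overall type 1 error level at 0.025 1-sided"). Equal Cui-Hung-Wang weights; maximum N 188, so stage 2 has 75 or 113 patients. The 20% dropout does not enter, since 150 is the evaluable number.

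**Formulas** (known-variance normal approximation, difference δ, SD σ).
- Stage means: θ1 = δ√75/(2σ) and θ2 = δ√n2/(2σ), with n2 = 75 or 113.
- Conditional power at N = 150 under the interim trend: CP = Φ(2·Z1 − 1.997/√0.5) = Φ(2·Z1 − 2.824).
- Power = P(Z1 > 2.605) + ∫ φ(z − θ1)·[1 − Φ(2.824 − z − θ2)] dz. The integral runs up to z = 2.605, from −∞ with no futility stop, or from z = (2.824 − 1.282)/2 = 0.771 if CP ≤ 10% stops the trial.

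**Check against the plan's own figures.** At 30 m, Table 22's interim Z of 2.598, 2.165 and 1.732 give CP of 0.991, 0.934 and 0.739, as printed. With an increase to 188 for every CP from 30% to 80% and no futility stop, power is 88.2% at 30 m/SD 60, 91.8% at 40 m/SD 75 and 71.3% at 30 m/SD 75. This matches >87%, >87% and 71%. Increasing only as far as 80% CP requires, capped at 188, gives 88.0% and 71.0% at 30 m with SD 60 and 75.

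**Power (%) by interim rule: no futility stop / CP ≤ 10% stop applied**

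| Difference, SD | Group sequential, N = 150 | Protocol Table 7 | SAP Table 35 | Whole 30-80% zone to 188 |
|---|---|---|---|---|
| 30 m, 60 | 85.9 / 82.8 | 86.5 / 83.4 | 87.0 / 83.9 | 88.2 / 85.1 |
| 30 m, 65 | 80.0 / 76.6 | 80.7 / 77.3 | 81.3 / 77.9 | 82.8 / 79.4 |
| 30 m, 70 | 73.9 / 70.3 | 74.7 / 71.1 | 75.4 / 71.7 | 77.1 / 73.5 |
| 30 m, 75 | 68.0 / 64.3 | 68.8 / 65.1 | 69.5 / 65.8 | 71.3 / 67.6 |

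Table 7 is read as going to 188 only when 188 brings CP to 80%. That needs Z1 ≥ (2.824 + 0.842)/(1 + √(113/75)) = 1.646, which is a CP of about 68% at N = 150, so few trials are enlarged. Table 35 enlarges from 57.2%.

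**Hand check at 30 m/SD 70.** Fixed N = 150: 30√150/(2×70) = 2.624, so power is Φ(2.624 − 1.960) = 74.7% at 0.025 and Φ(2.624 − 1.997) = 73.5% at 0.0229. Fixed N = 188: 30√188/140 = 2.938, giving 83.6% and 82.7%. Sending every continuing trial to 188 with no futility stop gives 82.4%. None reaches 87%.

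**Where 87% is lost at 30 m.** Fixed N = 150 at 0.025 needs 30√150/(2σ) ≥ 1.960 + 1.126 = 3.086, so σ ≤ 59.5 m. Across the four rules with no futility stop, the limit is about 59 to 61 m. Read as a range, the protocol's 50-75 m therefore fails from about 61 m upward even under the most favourable rule.

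**The case against.** The strongest reply is that the sentence was never meant as a continuous range. Neither document prints a power for 30 m/SD 70. Table 22 uses SDs of 50, 60 and 75, and the protocol twice prints 50 to 75. The SAP's own exception at SD 75 makes sense only if the range reaches 75. On that reading, 70 is probably a slip for 75, and the printed figures reproduce on the Table 22 grid. The sentence also discloses 71% at SD 75, which should warn a careful reader about SD 70. Finally, the prior-study SD in the Table 22 footnote is 38.7 m, from 20 patients, so SDs of 65-70 m may not arise.

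Most of this stands. A reader might infer that the sponsor simulated 30 m/SD 70 and miscalculated it, or that a printed power is 10 points too high. The documents do not support that: no such cell is printed, and the cells consistent with Table 22 reproduce.

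The reply does not rescue the wording. Nothing says that the >87% refers only to three SDs. Changing 70 to 75 would still leave the claim untrue at 30 m for SDs between about 61 and 75. How likely a large SD is does not bear on whether the power stated for it is right.

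**Conclusion.** The claim is over-general and inconsistent between documents; it is not a miscalculated figure. Against the stated 87%, power at 30 m with no futility stop is short by 4-7 points at SD 65 (80.0-82.8%) and 10-13 points at SD 70 (73.9-77.1%). The chance of missing a true 30 m effect is then about 17-20% and 23-26%. With the CP ≤ 10% stop applied, power is about 77-79% and 70-74%.

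Of the interim rules compared in the table, only the whole 30-80% zone to 188 with no futility stop gives both more than 87% at 30 m/SD 60 and 71% at 30 m/SD 75. That is neither Table 7 as written nor Table 35, and the match does not prove which rule was simulated. The group sequential design alone gives about 86% and 68% in those cells, so attributing the figures to both designs is slightly too favourable.

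A reader might also infer that the sample size is wrong. That does not follow: N = 150, rising to 188, is unaffected. The results assume a normal approximation with known SD, CP under the interim trend, CP rather than predictive power driving the rule, and no allowance for gains from the repeated-measures model. The documents do not say how futility was handled in the simulations.

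**What to change.** - Use one SD range in SAP 5.4, protocol 16.2 and the synopsis.
- Replace the range claim with a short table of power for each simulated combination of difference and SD, separately for the group sequential and re-estimation designs. Add 30 m with SD 65 and SD 70.
- Stop describing 30 m/SD 75 as the only exception.
- Reconcile protocol Table 7 and SAP Table 35 first, then run the table under the rule actually adopted and state whether the futility stop is applied. The values above should not be pasted in, because they depend on both choices.

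The cost is a short re-run of the existing simulation and rewording in three places. No patients are added and N does not change. The only downside is a less favourable stated power.

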**Table 22: Conditional and Predictive Power**

S.D	Mean Difference	Interim Z Statistics	Conditional Power (CP)	Predictive Power (PP) with vague prior#	Predictive Power (PP) with informative prior*
50	30	2.598	0.991	0.951	0.994
	40	3.464	$>0.999$	0.998	$>0.999$
	50	4.33	$>0.999$	$>0.999$	$>0.999$
	60	5.196	$>0.999$	$>0.999$	$>0.999$
	70	6.062	$>0.999$	$>0.999$	$>0.999$
60	30	2.165	0.934	0.853	0.974
	40	2.887	0.998	0.981	0.998
	50	3.608	$>0.999$	0.999	$>0.999$
	60	4.33	$>0.999$	$>0.999$	$>0.999$

S.D	Mean Difference	Interim Z Statistics	Conditional Power (CP)	Predictive Power (PP) with vague prior#	Predictive Power (PP) with informative prior*
	70	5.052	>0.999	>0.999	>0.999
75	30	1.732	0.739	0.669	0.912
	40	2.309	0.964	0.895	0.983
	50	2.887	0.998	0.981	0.998
	60	3.464	>0.999	0.998	>0.999
	70	4.041	>0.999	>0.999	>0.999

\*: The informative prior distribution on the treatment effect is based on estimates from a prior PAH study, in which analysis of change from baseline in 6 minute walk distance for 20 patients (7 controls, 13 treated) receiving oxygen for at least 12 hours a day yields an estimated treatment difference of 69.6 and pooled standard deviation estimate of 38.7.

#: Vague prior distribution which assumes no difference between groups.

All the sample size calculations were performed using EAST 6.4.

Using the above estimates yielded a planned sample size of 75 evaluable subjects per treatment arm (in total 150 subjects).

Further, in case the planned final analysis at N=150 (2 groups combined) is found not to have sufficient power, sample size increase could be made at IA up to a maximum of N=188 total patients (2 groups combined).

Assuming a 20% drop out rate, a total of 188 subjects (94 per treatment arm) are planned to support 150 at final analysis, with the ability to go up to 226 subjects (113 per treatment arm) to support 188 at final analysis, based on the sample size reassessment at the interim analysis.

As subjects must achieve a satisfactory adherence to the INOpulse delivery device, a dynamic randomization system will be used to ensure that approximately 94 (or 113) subjects per treatment cohort comply with the adherence criteria at Week 2. Enough subjects will be recruited such that a minimum sample size of 150 (or 188) subjects will complete 18 weeks of treatment on the INOpulse delivery device.

Subjects who do not comply with the required device adherence, as well as who do not meet the study entry criteria at Week 2, will be withdrawn from the study and replaced.

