## 8.0 Interim Analysis

A formal interim analysis is planned in this study as follows:

1. Stop for futility (null hypothesis is accepted; there is no difference between iNO and Placebo).
2. Stop for efficacy (null hypothesis is rejected; there is difference between iNO and Placebo favoring iNO).
3. Sample size determination.
4. Stop in case of safety concerns. Safety concerns may be some imbalances in adverse events frequency which is not in favor of iNO. No formal statistical guideline is provided for this purpose, the sponsor relies on the medical expertise of DMC members.
5. Continue the trial with the planned sample size until next stage if point 1, 2 or 4 not apply.

The following two designs will define the interim analysis strategy:

- 1) Design 1: Groups Sequential Design (for efficacy part)
- 2) Design 2: Sample Size Re-estimation (SSR) (for futility and sample size re-estimation)

The interim analysis schedule planned as follows:

Schedule	Requirement
1 st	After 75 patients complete 18 Weeks of blinded treatment phase.
Final	After 150/188 (depending on CP and PP) patients complete 18 Weeks of blinded treatment phase.

Traditional group sequential design (GSD) alpha spending function  $\Gamma = -3$  ([Hwang, Shih, deCani, 1990](#)) is used to control the overall type 1 error at 0.025, 1-sided. The interim analysis rule ([Table 35](#)) is as follows.

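### SAP 5.4 inflates for one 20% dropout rate in two different ways: 226 subjects support about 181 completers, and 188 completers need 235 (236 for equal arms)

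*SAP*

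**What the plan says.** **Enrolment.** SAP section 5.4 (the text after Table 22) plans 150 evaluable subjects and allows that a "sample size increase could be made at IA up to a maximum of N=188 total patients (2 groups combined"). It assumes 20% dropout, gives 188 enrolled (94 per arm) for 150 at the final analysis, and continues "with the ability to go up to 226 subjects (113 per treatment arm) to support 188 at final analysis". It then says that the randomisation system will ensure that "approximately 94 (or 113) subjects per treatment cohort comply with the adherence criteria at Week 2", and commits: "Enough subjects will be recruited such that a minimum sample size of 150 (or 188) subjects will complete 18 weeks of treatment". SAP section 8.0 times the final analysis by completers: "After 150/188 (depending on CP and PP) patients complete 18 Weeks of blinded treatment phase".

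**Power.** For 150 patients and differences of 30 to 70 m, SAP 5.4 has a "standard deviation from 50-70 meters yielded" more than 87% "power for both designs (for all cases except the most extreme case (mean difference of 30 meters and S.D 75", where the figure is 71%). Protocol section 16.2 gives "standard deviations from 50 to 75 meters yielded >87% power for all cases except the most extreme case", again about 71% at 30 m / SD 75, and the synopsis agrees. The protocol does not attribute these figures to two designs.

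**The concern.** One sentence states one dropout rate and two enrolment targets, and the two targets do not follow from the same rule. If the upsized figure is too small, the section contradicts itself: it names a number enrolled that does not deliver, at its own dropout rate, the number it says will complete. The protocol gives an enrolment figure only for the 150-completer case, so 226 is the only enrolment figure for the upsized trial.

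The power sentence raises a related question. It credits one set of figures to both the group sequential design and the re-estimation design. The second can add up to 38 subjects and the first cannot, so the two should not share the same power. The SAP's SD range also stops at 70, while its named exception is at SD 75.

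**Working it through.** **Dropout**

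Inputs from SAP 5.4: dropout d = 0.20; targets 150 and 188; stated enrolments 188 and 226.

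1. Base case, N/(1−d): 150/0.80 = 187.5, so 188. The stated figure is reproduced. The other rule, N × (1+d), would give 150 × 1.2 = 180, which is not what is stated.
2. Upsized case, same rule: 188/0.80 = 235. Per arm, 94/0.80 = 117.5, so 118, or 236 in total. The stated 226 is not reproduced.
3. Upsized case, other rule: 188 × 1.2 = 225.6, so 226; per arm 94 × 1.2 = 112.8, so 113. This reproduces both stated figures.
4. Yield at 20% dropout: 226 × 0.80 = 180.8 in total; 113 × 0.80 = 90.4 per arm against the 94 needed. By contrast 236 × 0.80 = 188.8.
5. Dropout at which 226 is enough: 1 − 188/226 = 16.8%.

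**Power (secondary)**

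Inputs: interim at 75 and final at 150 patients, 1:1; one-sided boundaries p < 0.0046 (z = 2.6045) and p < 0.0229 (z = 1.9972), from SAP Table 35; equal stage weights. SD is treated as known, with no covariate adjustment and no futility stop.

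*Scale check against Table 22.* Interim Z = difference/(SD × √(4/75)). At 30 m this is 2.165 for SD 60 and 1.732 for SD 75, as tabulated. Conditional power at the observed trend is Φ(2·z1 − √2 × 1.9972), which gives 0.934 and 0.739, also as tabulated.

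*Group sequential design, N = 150.* Power = P(Z1 > 2.6045 or Z2 > 1.9972), where Z1 and Z2 are the interim and final cumulative statistics with correlation √0.5.

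*Single look at N = 150 with the full 0.025.* Power = Φ(30/(SD × √(4/150)) − 1.960). On this scale it is an upper limit for any group sequential design with that alpha and maximum N.

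*Re-estimation design.* Second stage 75, or 188 − 75 = 113 when interim conditional power lies in 30–80% (z1 from 1.150 to 1.833). The final statistic is (z1 + z2)/√2, with z2 the second-stage statistic, integrated over z1.

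| Power at 30 m | SD 60 | SD 70 | SD 75 |
|---|---|---|---|
| Stated | >87% | – | 71% |
| Group sequential, N = 150 | 85.9% | 73.9% | 68.0% |
| Single look, N = 150 | 86.5% | 74.7% | 68.8% |
| Re-estimation, whole 30–80% zone raised to 188 | 88.2% | 77.1% | 71.3% |

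At SD 50 the group sequential design gives 95.4% for 30 m, and at SD 75 it gives 90.0% for 40 m. The shortfall against the stated figures is therefore confined to 30 m with the larger SDs.

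**The case against.** **The completer commitment neutralises the slip.** Recruitment is to continue until 188 complete, the final analysis is triggered by completers, and the Week 2 target is only approximate. This stands, and it is why the point is minor. It does not make 226 consistent with 188 at 20% dropout.

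**The power gap is small and may be only wording.** At SD 60 the shortfall is about one point against a simulated figure. SAP 8.0 presents the two designs as jointly defining the interim strategy, so the reference to both could mean the combined procedure, which does give 88.2% and 71.3%. The primary model also adjusts for baseline 6MWD: covariates explaining about 3% of variance would lift the group sequential figure at SD 60 to 87%, and about 7% would lift the SD 75 figure to 71%. All of this is fair. The upper limit quoted above holds only for an unadjusted comparison with known SD. But Table 22 uses that unadjusted scale, no covariate gain is mentioned beside the power statement, and the 71% is three points above the group sequential value. The sentence needs clarifying.

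**Stronger readings that the documents do not support:**
- *The upsized trial would be analysed with 181 subjects.* The completion commitment says otherwise.
- *Sites, supply or ethics submissions rest on 226.* That figure appears only in the SAP; the protocol plans 188.
- *The correction means ten more randomised.* SAP 5.4 attaches 94 and 113 to subjects who pass the Week 2 adherence check, and run-in failures are replaced. The number randomised exceeds 226 or 236 by a run-in failure rate that is not stated.
- *The power simulations used Table 22's SDs of 50, 60 and 75.* Table 22 lists interim conditional and predictive power; neither document says that the simulations used the same values.
- *The quoted power is wrong because it omits the futility stop.* Neither document says whether it does. The rule refers to conditional or predictive power without naming which prior applies, so no single with-futility figure follows.

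**Conclusion.** The dropout inconsistency is certain and needs no assumption beyond the SAP's own 20%: 226 is 9 short of 235 and 10 short of 236, and it supports about 181 completers. The consequence is minor. Even if enrolment did stop at 226 and 181 completed, overall power under Table 35 without futility would fall by only 0.1 to 0.3 points at 30 m (SD 60 to 75). Type I error control, boundaries and the planned analysis do not depend on the enrolment figure.

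The power point is secondary and conditional on the unadjusted, known-SD scale of Table 22 without futility. On that scale the stated >87% and 71% match the re-estimation design with its whole 30–80% zone upsized, and do not match the group sequential design. That the figures were carried over from one design to both is an inference. The re-estimation figures themselves are not in dispute.

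The SD wording fails on either document's range. The SAP's 50–70 excludes its own SD 75 exception, and both ranges include SD 70, where 30 m gives only about 74–77%. A claim of more than 87% everywhere except SD 75 cannot hold over a continuous range.

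**What to change.** In SAP 5.4:

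1. Replace 226 (113 per arm) by 236 (118 per arm) as the enrolment for 188 at the final analysis, and make the Week 2 target 94 (or 118). If 226 is meant as a ceiling, keep it and state that it supports 188 only at dropout of 16.8% or less, and about 181 at 20%.
2. Say that these are counts after the Week 2 check, so the number randomised will be higher.
3. Leave the design maximum of 188 unchanged throughout, including Table 35.
4. Remove the attribution of the power figures to both designs, or report the group sequential figures separately (85.9% at 30 m / SD 60; 68.0% at 30 m / SD 75, on the scale used here).
5. Replace the SD range by the SD values actually simulated, and do the same in Protocol 16.2 and the synopsis. State whether the quoted power includes the futility stop.

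The cost is text only. The 236 adds nothing to the existing commitment to 188 completers. It means 10 more subjects past Week 2 than the current figure, and only if the trial is upsized.
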